5.3.1.2 Collection and Handling of Optional Samples for Exploratory Research and Validation Studies

Subjects will have the option to provide samples for exploratory research and validation studies. Subjects may still participate in the main study even if they decide not to participate in this optional exploratory research/validation study.

Exploratory research can help to improve AbbVie's understanding of how individuals respond to drugs and the ability to predict which subjects would benefit from receiving specific therapies. In addition, exploratory research may help to improve the understanding of how to diagnose and assess/monitor AS by assessing [REDACTED]

Validation studies, including those related to the development of [REDACTED], may be carried out retrospectively in order to assess associations between [REDACTED]

AbbVie (or people or companies working with AbbVie) will store the [REDACTED] exploratory research/validation studies samples in a secure storage space with adequate measures to protect confidentiality. The samples will be retained while research on upadacitinib (or drugs of this class) or AS and related conditions continues, but for no longer than 20 years after study completion.

[REDACTED] will be collected at the visits indicated in [Appendix F](#) from each subject who consents to provide samples for exploratory/validation research. The procedure for obtaining and documenting informed consent is discussed in Section 9.3.

Samples will be shipped frozen to AbbVie or a designated laboratory for [REDACTED] and/or long-term storage or analyses. Instructions for the preparation and shipment of the [REDACTED] will be provided in a laboratory manual.

[REDACTED] will be collected at the visits indicated in [Appendix F](#) from each subject who consents to provide samples for exploratory/validation research. The procedure for obtaining and documenting informed consent is discussed in Section 9.3.

Samples will be shipped to AbbVie or a designated laboratory for [REDACTED] and/or long-term storage or analyses. Instructions for the preparation and shipment of the samples will be provided in a laboratory manual.

[REDACTED] will be collected at the visits indicated in [Appendix F](#) from each subject who consents to provide samples for exploratory/validation research. These

samples may be used for [REDACTED] if needed. The procedure for obtaining and documenting informed consent is discussed in Section 9.3.

Samples will be shipped to AbbVie or a designated laboratory for long-term storage and/or analyses. Instructions for the preparation and shipment of the samples will be provided in a laboratory manual.

5.3.2 Drug Concentration Measurements

5.3.2.1 Collection of Samples for Analysis

Blood samples for assay of upadacitinib and possibly other concomitant medications will be collected as follows:

- Weeks 2 and 4 prior to dosing;
- Weeks 8, 12, 14, 24, 52, 76, and 104/PD at any time during the visit.

On Week 2 and Week 4 visit days, if possible, subjects should take the study drug dose at the clinic after collecting the PK blood sample, except if the subjects regularly take the study drug dose at night. Those subjects who regularly take the study drug dose at night should continue to take study drug according to their normal schedule. For all other visits, subjects can take the study drug dose on visit days at their regular schedule and not necessarily at the clinic.

The date and accurate time of the PK sample collection will be recorded on the lab requisition form. The date and accurate time of the last two study drug doses will be recorded on the eCRF to the nearest minute.

Refer to the study specific laboratory manual for detailed instructions on sample collection, processing, and shipment.

5.3.2.2 Measurement Methods

Plasma concentrations of upadacitinib will be determined by the Drug Analysis Department at AbbVie using a validated liquid chromatography/mass spectrometry method.

5.3.3 Efficacy Variables

5.3.3.1 Primary Variable

The primary endpoint is the proportion of subjects with ASAS 40 response at Week 14, which is defined as a $\geq 40\%$ improvement and an absolute improvement of ≥ 2 units (on a scale of 0 to 10) from Baseline in at least three of the following four domains, with no worsening at all in the remaining domain:

- Patient's Global Assessment – Represented by the PtGA NRS score (0 to 10);
- Pain – Represented by the Patient's Assessment of Total Back Pain NRS score (0 to 10);
- Function – Represented by the BASFI NRS score (0 to 10);
- Inflammation – Represented by the mean of the two morning stiffness-related BASDAI NRS scores (mean of items 5 and 6 of the BASDAI [0 to 10]).

5.3.3.2 Secondary Variable

The key multiplicity adjusted secondary efficacy endpoints (upadacitinib versus placebo unless noted otherwise) at Week 14 are:

1. Change from Baseline in Ankylosing Spondylitis Disease Activity Score (ASDAS);
2. Change from Baseline in MRI Spondyloarthritis Research Consortium of Canada (SPARCC) score (Spine);
3. Proportion of subjects with BASDAI 50 response (defined as 50% improvement in the Bath AS Disease Activity Index);

4. Change from Baseline in AS QoL;
5. Proportion of subjects with ASAS partial remission (PR) (defined as an absolute score of ≤ 2 units for each of the four domains identified in ASAS 40);
6. Change from Baseline in BASFI;
7. Change from Baseline in BASMI_{lin};
8. Change from Baseline in MASES;
9. Change from Baseline in WPAI;
10. Change from Baseline in ASAS HI.

Additional key secondary endpoints (upadacitinib versus placebo) are:

- ASAS 20 response at Week 14;
- Change from Baseline in MRI SPARCC score (SI joints) at Week 14.

5.3.3.3 Additional Variables

Additional endpoints are the following measurements assessed in subjects treated with upadacitinib versus placebo at scheduled time points other than those specified for the primary and key secondary variables:

- Proportion of subjects with:
 - ASAS 20 response;
 - ASAS 40 response;
 - ASAS PR;
 - ASAS 5/6 (20% improvement from Baseline in five out of the following six domains: BASFI, patient's assessment of total back pain, PtGA, inflammation [mean of items 5 and 6 of the BASDAI] lateral lumbar flexion from BASMI_{lin}, and high sensitivity CRP [hsCRP]);
 - ASDAS Inactive Disease (ASDAS score < 1.3);
 - ASDAS Major Improvement (change from Baseline at least 2.0);

- ASDAS Clinically Important Improvement (change from Baseline of at least 1.1).
- Change from Baseline in:
 - ASAS HI;
 - ASDAS;
 - AsQoL;
 - BASDAI;
 - BASFI;
 - BASMI_{lin};
 - CRP;
 - Dactylitis;
 - FACIT-F;
 - ISI;
 - MASES;
 - Modified Stoke Ankylosing Spondylitis Spine Score (mSASSS) score with conventional radiograph;
 - MRI SPARCC score of SI joints;
 - MRI SPARCC score of Spine;
 - Patient's Assessment of Total Back Pain;
 - Patient's Assessment of Nocturnal Back Pain;
 - Patient's Global Assessment of Pain;
 - PGA;
 - PtGA;
 - TJC and SJC;
 - WPAI.

Evaluation of structural changes in the spine will be explored in subjects who are participating in the low-dose CT scan substudy using a scoring system for syndesmophytes.

5.3.4 Safety Variables

Safety evaluations include AE monitoring, physical examinations, vital sign measurements, and clinical laboratory testing (hematology, chemistry, and urinalysis) as a measure of safety and tolerability for the entire study duration.

5.3.5 Pharmacokinetic Variables

Plasma upadacitinib concentrations will be obtained at the times indicated in [Appendix E](#). A non-linear mixed-effects modeling approach will be used to estimate the population central values and the empirical Bayesian estimates of the individual values of upadacitinib oral clearance (CL/F) and volume of distribution (V/F). Additional parameters may be estimated if useful in the interpretation of the data.

5.3.6 Exploratory Research Variables and Validation Studies

Optional samples may be collected to conduct exploratory investigations into [REDACTED]. The types of [REDACTED] to be analyzed may include but are not limited to [REDACTED].

[REDACTED] may be used to assess and generate [REDACTED]. These assessments may be explored in the context of [REDACTED]. The results from these analyses are exploratory in nature and may not be included with the clinical study report (CSR).

The samples may also be used to [REDACTED]. In addition, samples from this study may be stored for future use. Samples may then be used to validate [REDACTED].

5.4 Removal of Subjects from Therapy or Assessment

5.4.1 Discontinuation of Individual Subjects

Subjects can request to be discontinued from participating in the study at any time for any reason, including but not limited to lack of response to treatment. The Investigator may discontinue any subject's participation for any reason, including an AE, safety concerns, lack of efficacy, or failure to comply with the protocol. See Section 6.1.7 for toxicity management criteria.

Subjects will have study drug treatment discontinued immediately if any of the following occur:

- Clinically significant abnormal laboratory results or AEs that rule out continuation of the study drug, as determined by the Investigator or the AbbVie TA MD.
- Serious infections (e.g., sepsis) that cannot be adequately controlled within 2 weeks by anti-infective treatment or would put the subject at risk for continued participation in the trial as determined by the Investigator.
- The Investigator believes it is in the best interest of the subject.
- The subject requests withdrawal from the study.
- Inclusion or exclusion criteria violation was noted after the subject started the study drug, when continuation of the study drug would place the subject at risk as determined by the AbbVie TA MD.
- Introduction of prohibited medications or dosages when continuation of the study drug would place the subject at risk, as determined by the AbbVie TA MD.
- Subject is non-compliant with TB prophylaxis (if applicable) or develops active TB at any time during the study.
- The subject becomes pregnant while on study drug.
- Malignancy, except for localized NMSC or carcinoma in situ of the cervix.

- Subject is significantly non-compliant with study procedures, which would put the subject at risk for continued participation as determined by the Investigator.
- Subject develops a gastrointestinal perforation.
- Subjects not responding to treatment are to be withdrawn from the trial based on Investigator's discretion.
- Starting at Week 24, subjects who still do not achieve at least an ASAS 20 response at two consecutive visits will be discontinued from study drug treatment.
- Confirmed diagnosis of deep vein thrombosis, pulmonary embolus, or non-cardiac, non-neurologic arterial thrombosis.

In order to minimize missing data for efficacy and safety assessments, subjects who prematurely discontinue study drug treatment should complete a PD visit as soon as possible, preferably within 2 weeks. Afterwards, subjects should continue to be followed for all regularly scheduled visits as outlined in [Appendix E](#) and adhere to all study procedures except for dispensing study drug, PK sample collection, blood sample collection for optional exploratory research and validation studies, and x-rays. (New x-rays are dependent on the time of discontinuation; refer to Section 5.3.1.1 for details.) In addition, all future efficacy-driven discontinuation criteria no longer apply (ASAS 20 response). Subjects should be advised on the continued scientific importance of their data even if they discontinue treatment with study drug early.

If a subject prematurely discontinues study participation (withdrawal of informed consent), the procedures outlined for the PD visit should be completed as soon as possible, preferably within 2 weeks. In addition, a 30-day follow-up visit (or phone call if a visit is not possible) should occur to determine the status of any ongoing AEs/SAEs or the occurrence of any new AEs/SAEs. Subjects who discontinue the study prematurely after randomization will not be replaced.

All attempts must be made to determine the date of the last study drug dose and the primary reason for discontinuation of study drug or study participation. The information

will be recorded on the appropriate eCRF page. However, these procedures should not interfere with the initiation of any new treatments or therapeutic modalities that the Investigator feels are necessary to treat the subject's condition. Following discontinuation of study drug, the subject will be treated in accordance with the Investigator's best clinical judgment, irrespective of whether the subject decides to continue participation in the study.

Lost to Follow-Up

For subjects to be considered lost to follow-up, reasonable attempts must be made to obtain information on the final status of the subject. At a minimum, two phone calls must be made, and one certified letter must be sent and documented in the subject's source documentation.

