Period 1 will begin at the Baseline Visit (Day 1) and will end at the Week 14 Visit. At the Baseline Visit, subjects who meet all the inclusion criteria and none of the exclusion criteria described in Section 5.2.1 and Section 5.2.2 will be enrolled into the study and randomized to double-blind treatment. During this period of the study, subjects will visit the study site at Weeks 2, 4, 8, 12, and 14. A ± 3 day window is permitted around scheduled study visits. The last dose of oral study drug in Period 1 is taken the day prior to the Week 14 visit.

Period 2 (90-Week Open-Label Extension Period)

Period 2 will begin at the Week 14 visit after all assessments have been completed. At Week 14, subjects on placebo will receive open-label upadacitinib 15 mg QD. Subjects on upadacitinib 15 mg QD will continue to receive the same treatment in an open-label manner. During Period 2, subjects will have a study visit at Weeks 16, 20, 24, 32, 40, 52, 64, 76, 88, 96, and 104. A ± 7 day window is permitted around scheduled study visits. Starting at Week 24, subjects who do not achieve at least an ASAS 20 response compared with Baseline at two consecutive visits will be discontinued from study drug treatment (see Section 5.4.1).

Discontinuation of Study Drug and Continuation of Study Participation

Subjects may discontinue study drug treatment, but may choose to continue to participate in the study (refer to Section 5.4.1 for additional details). Subjects who prematurely discontinue study drug should complete a Premature Discontinuation (PD) Visit as soon as possible, preferably within 2 weeks. Afterwards, subjects should follow the regular visit schedule and adhere to all study procedures except for dispensing study drug, pharmacokinetic (PK) sample collection, and blood sample collection for optional exploratory research and validation studies. In addition, future ASAS 20 nonresponse discontinuation criteria no longer apply. If at any point a subject no longer wants to provide assessments (withdrawal of informed consent) following discontinuation of study drug, a second PD visit is not required.

Premature Discontinuation of Study (Withdrawal of Informed Consent)

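### Protocol 5.4.1 lets sites end trial participation, not just study drug, for non-response, against its own follow-up policy; the loss falls on As Observed, tipping-point and Period 2 data, not on the primary result

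*Protocol*

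**What the plan says.** Protocol 5.4.1 opens with a general permission: "The Investigator may discontinue any subject's participation for any reason, including an AE, safety concerns, lack of efficacy", among other reasons. It then introduces a list with "Subjects will have study drug treatment discontinued immediately if any of the following occur". Two adjacent bullets in that list deal with non-response:

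- "Subjects not responding to treatment are to be withdrawn from the trial based on Investigator's discretion". No week and no definition of non-response are given.
- "Starting at Week 24, subjects who still do not achieve at least an ASAS 20 response at two consecutive visits will be discontinued". What ends under this bullet is the drug, not participation.

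The paragraph after the list sets the follow-up policy: "In order to minimize missing data for efficacy and safety assessments, subjects who prematurely discontinue study drug treatment should complete a PD visit", and then "Afterwards, subjects should continue to be followed for all regularly scheduled visits". Protocol 5.1 agrees: "Subjects may discontinue study drug treatment, but may choose to continue to participate in the study". Both sections describe ending study participation as withdrawal of informed consent, which is the subject's act rather than the investigator's.

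The SAP treats these data in three ways:

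- **Primary ASAS 40 analysis (9.1.2, 9.2.1).** Response requires not having stopped study drug by Week 14. Stopping drug, or a missing value, counts as non-response.
- **MMRM for the continuous key secondary endpoints (9.1.2, Appendix D).** Data collected after stopping drug are excluded.
- **As Observed supplementary analyses (9.2.2, 9.2.3) and the tipping-point analyses (Appendix E).** Off-drug values are used. A subject without a value is left out of the As Observed analysis.

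**The concern.** The non-response bullet names a different event from the heading above it, the bullet beside it and the follow-up paragraph below it. Those three concern study drug; this one removes the subject from the trial. Two sites with the same poorly responding subject could therefore act differently, and both could cite the protocol. One would end all visits. The other would stop drug and keep the subject on schedule.

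Subjects removed in this way are selected on outcome, and possibly in unequal numbers by arm. The As Observed estimands are defined regardless of drug discontinuation and serve as a check on the primary and ranked results. They need the off-drug values that continued follow-up was written to secure.

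**Working it through.** **1. The plan's own figure.** Inputs (Protocol 8.2, SAP 4.3): placebo ASAS 40 rate 20%, difference 26 points (so 46% on upadacitinib), two-sided 0.05, at least 90% power, 10% dropout, 170 subjects at 1:1.

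n per arm = [z₀.₉₇₅√(2p̄q̄) + z₀.₉₀√(p₀q₀ + p₁q₁)]² / d², with p̄ = 0.33:

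(1.960 × 0.665 + 1.282 × 0.639)² / 0.26² = 4.504 / 0.0676 = 66.6, so 67 per arm. The continuity correction gives 75; 75 / 0.90 = 83.3, so 84 per arm, or 168 in total. With 0.90 × 85 = 76.5 evaluable per arm, power is 93.6% (about 91% with the correction). The stated 170 is reproduced, and nothing below changes it.

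**2. Primary analysis.** Expected responders are 0.20 × 85 = 17 on placebo and 0.46 × 85 = 39.1 on upadacitinib. Anyone taken out of the trial has also stopped drug, so is a non-responder whether followed or not, and both denominators stay at 85. The difference is 39.1/85 − 17/85 = 26 points in either case.

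**3. MMRM.** Off-drug values are excluded even when collected, so ending participation rather than drug alone changes nothing.

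**4. As Observed ASAS 40.** Assume shares w₀ (placebo) and w₁ (upadacitinib) leave the trial, and that all of them would have been non-responders at Week 14. Then

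difference = 0.46/(1 − w₁) − 0.20/(1 − w₀).

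| w₀ | w₁ | Placebo | Upadacitinib | Difference (points) |
|---|---|---|---|---|
| 0% | 0% | 20.0% | 46.0% | 26.0 |
| 5% | 0% | 21.1% | 46.0% | 24.9 |
| 10% | 0% | 22.2% | 46.0% | 23.8 |
| 10% | 5% | 22.2% | 48.4% | 26.2 |
| 10% | 10% | 22.2% | 51.1% | 28.9 |
| 20% | 5% | 25.0% | 48.4% | 23.4 |
| 20% | 10% | 25.0% | 51.1% | 26.1 |

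With full follow-up every row would read 26.0. The shift runs from −2.6 to +2.9 points, and its sign depends on the balance between arms.

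**5. Which Week 14 values are exposed (SAP 5.2).** The ASAS component window opens on Day 93, so an earlier premature-discontinuation visit cannot supply a Week 14 value. The BASMI and WPAI window opens on Day 2 and the MRI window on Day 4. For these endpoints an early discontinuation assessment can stand as the Week 14 value. The problem is then an early value in place of one nearer Day 99, not necessarily a missing one.

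**6. Period 2, with drug stopped in both cases.**

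| Item | Stays in the study | Leaves the study |
|---|---|---|
| As Observed efficacy (SAP 9.3) | Later visits contribute | None after the discontinuation visit |
| Spine x-ray if drug stops before Week 76 (Protocol 5.3.1.1) | Taken at Week 104 | None after screening |
| Adverse events beyond 30 days off drug (Protocol 6.1.4) | Collected for remaining participation | Not collected |

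Subjects who stop at or after Week 76 have the x-ray at the discontinuation visit in both cases.

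**The case against.** The strongest reply is that the section can be read as a whole. The list is about study drug, the next paragraph keeps those subjects in follow-up, and leaving the study means withdrawing consent. On that reading the bullet is loose wording. This is a fair account of the likely intent. It does not bind a site, though, because the bullet says trial and the opening paragraph separately allows participation to end for lack of efficacy.

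Three stronger readings are tempting, and the documents do not support them.

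- **That the two non-response rules contradict each other on timing.** The bullet does not say that withdrawal may happen at any time; it simply gives no week. The Week 24 rule does not say that drug may be stopped for non-response only from then. One is discretionary and the other mandatory, so they can coexist. The firm conflict is trial versus study drug.
- **That the primary result loses Week 14 outcomes or is biased by the withdrawals.** Steps 2 and 3 show that ending participation adds nothing to what stopping drug already does.
- **That BASMI, WPAI and MRI values would be missing in proportion to the withdrawals.** A discontinuation visit is requested even from subjects who leave the study, MRI is to be attempted within 14 days of it, and the SAP windows can map those values to Week 14.

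Two further replies stand in part. The tipping-point analysis already varies the missing ASAS 40 outcomes, which limits the damage, but withdrawals enlarge the number missing and so widen the range it must cover. And the Period 2 efficacy analyses carry no hypothesis tests, so no formal conclusion there is at risk.

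**Conclusion.** The inconsistency is real and its reach is limited. Protocol 5.4.1 allows a poor responder's participation to end where the rest of the section, and 5.1, expect only study drug to end.

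- **Not affected:** the primary ASAS 40 analysis and the MMRM analyses.
- **Affected:** the As Observed supplementary estimands, the tipping-point analyses built on As Observed data, Period 2 As Observed efficacy, the Week 104 spine x-ray for subjects who stop before Week 76, and adverse-event collection beyond 30 days off drug.

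The only figure is the As Observed ASAS 40 range of 23.4 to 28.9 points against 26. It rests on assumed withdrawal shares, which the documents do not give, and on treating every withdrawn subject as a true non-responder.

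SAP section 11.0 puts the Week 14 lock in February 2019, and this protocol version is dated 20 December 2019. A wording change therefore cannot recover Period 1 data. It could still act on Period 2, for which the August 2020 SAP plans a Week 104 lock.

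**What to change.** Label: cheap improvement.

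- Reconcile the non-response bullet, and the permission in the opening paragraph of 5.4.1 to end participation for lack of efficacy, with the list heading, the follow-up paragraph of 5.4.1 and the discontinuation text in 5.1. A stop for non-response should be recorded as a study drug discontinuation, with scheduled follow-up continuing unless the subject withdraws consent.
- Leave the investigator's authority to end participation for safety or non-compliance as it stands.
- For Week 14, report by arm how many subjects ended participation for lack of efficacy, next to the As Observed and tipping-point results. SAP 7.0 already summarises reasons separately for study drug and study participation, so this needs no new data.

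This point takes no position on when, or on what criterion, a non-responder should stop treatment.

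The cost is a short protocol clarification and a few more off-drug visits, of a kind the protocol already plans for other subjects who stop drug.
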